5.2. Handling of Dropouts, Missing Data, and Outliers

5.2.1. Handling of Missing Efficacy Data

Participants with missing PSA data at the Month 8 visit will have a durable PSA response imputed if they have a confirmed PSA response at the latest non-missing PSA collection preceding the Month 8 visit and the first non-missing PSA collection following the Month 8 visit. Otherwise, if participants are missing PSA data at Month 8, they will be treated as non-responders for the main analysis. A confirmed PSA response is defined as a $\geq 50\%$ reduction in serum PSA compared to baseline and measured twice consecutively, at least 2 weeks apart. Details regarding the analyses of PSA are provided in Section 6.6.

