11.2.3 Secondary Endpoint Analyses

11.2.3.1 PSA Response to VTP-850

The number, proportion, and 90% confidence interval (CI) of participants with a PSA response, defined as $\geq 50\%$ reduction in serum PSA compared to baseline and measured twice consecutively, will be summarised by timepoint and overall. This will be further broken down by whether the participants had prior radical prostatectomy or prior external beam radiation. The maximum PSA reduction from baseline will be summarised, as well as by whether participants had prior radical prostatectomy, external beam radiation or brachytherapy.

11.2.3.2 Durable PSA Response to VTP-850 at Month 8

The number, proportion and 90% CI of participants with a durable PSA response at Month 8 will be summarised, among all participants and among those with a response by Month 6. Durable PSA response is defined as having follow-up through Month 8 and a confirmed PSA response without having PSA progression (i.e., an increase relative to nadir of $\geq 25\%$ and an absolute increase of 0.2 ng/mL or more) on or before Month 8. This will be further summarised by whether the participants had prior radical prostatectomy, external beam radiation or brachytherapy.

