2.2.2.1. Endpoints for the Secondary Objective(s)

The following are the relevant endpoints corresponding to the secondary objectives in the phase 1 part of this study:

- Percentage of participants with $\geq 50\%$ reduction in serum PSA compared to baseline at any time, based on two consecutive measurements at least 2 weeks apart
- Percentage of participants with confirmed PSA response compared to baseline without having PSA progression on or before Month 8

Full details for each endpoint are provided in Section 6.6.2.

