2.5. Secondary Efficacy Variable(s)

Prostate-specific antigen (PSA) is measured using blood samples for high-sensitivity serum PSA and is assessed at the central laboratory. Samples are collected at Screening, baseline (Day 1), Day 29, 57, 64, 91 and then in monthly intervals from Months 4 to 12 and then every 2 months to Month 24. Measurements from Months 7 to 24 are only made if a participant has a PSA response within the first 6 months and only until the start of new therapy such as ADT or development of unequivocal metastatic prostate cancer. Baseline PSA is defined using the

rules for baseline specified in Section 5.1.2. PSA response and progression are defined in Section 6.6.2. Missing values will not be imputed.

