5.1.4. Visit Windows

Tables 5 to 7 provides the relative study day ranges to be applied to the assessment / sample collection date to derive the analysis timepoint for by timepoint analyses of PSA / laboratory / vital signs and symptom-directed physical examination.

The following considerations are to be followed when deriving the analysis timepoints:

- The relative day number of the assessment lies between the lower and upper boundary of the visit window (the boundary values are included)
- Both scheduled and unscheduled assessments are included for visit windowing
- If there are two or more valid assessments for a defined window the following rules will be applied:
 - Assessments with missing data and assessments marked “Not Done” will be considered as providing a missing response and are not permitted to be assigned to a visit window.
 - The worst value (e.g. out of reference range preferred to within range; abnormal preferred to normal) will be used in each window. If multiple assessments fall within the same window with equal value, then the first non-missing value will be used for the summary.
- Participants who have an optional third dose of MVA-PCAQ due to an initial PSA response followed by progression will have an additional day 57, 64 and 71 visit. If two assessments are in both the additional day 64 and day 91 visit window or day 71 and day 91 visit window then the first assessment will be assigned to day 64 or 71 and the second to day 91. If only one assessment is available in both windows then this will be assigned to day 91.
- Participants who have had a study pause will not have visit windowing applied for visits after this window and will have analysis visit assigned based on the recorded visit name in the eCRF.

Table 4: Definition of Visit Windows for PSA Assessments

Period	Visit	Target Day of Visit	Protocol Visit Windows	Analysis Visit Window
Screening	Screening	Day -1 ^a	Day -43 to -1	Not Applicable
Intervention	Baseline	Day 1 ^a	Day 1 ^a	Prior to or on Day 1 ^a
Intervention	Day 29	Day 1 ^b	Day 1 ^b	Day 1 ^b
Intervention	Day 57	Day 1 ^c	Day 1 ^c	Day 1 ^c
Intervention	Day 64	Day 8 ^c	Day 5 to 9 ^c	Day 2 to 14 ^c
Intervention	Additional Day 57	Day 1 ^d	Day 1 ^d	Day 1 ^d
Intervention	Additional Day 64	Day 8 ^d	Day 5 to 9 ^d	Day 2 to 14 ^d
Intervention	Day 91	Day 91 ^a	Day 89 to 91 ^a	Day 78 to 104 ^a
Short-Term Follow-Up	Month 4	Day 120 ^a	Day 113 to 127 ^a	Day 105 to 135 ^a

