6.6.2. Secondary Efficacy Analysis

6.6.2.1. PSA Response to VTP-850

The number, proportion and 90% confidence intervals (CI) of participants with a confirmed PSA response, defined as a $\geq 50\%$ reduction in serum PSA compared to baseline and measured twice consecutively, at least 2 weeks apart, will be summarized by timepoint (using visit windows defined in Section 5.1) and overall for each treatment group using the EES. The proportion at each time point will present the participants who have the 1st (if confirmed at least 2 weeks later) measurement where the $\geq 50\%$ reduction in serum PSA has been met compared to baseline. Percentage change in PSA will be calculated as $100 \times (\text{PSA value (ng/ml) at visit } i - \text{PSA value at baseline}) / (\text{PSA value at baseline})$. The 90% CIs will be calculated using Jeffrey's confidence limits. The maximum percentage change in PSA from baseline will be summarized continuously by treatment group. A waterfall plot of maximum percentage change in PSA from baseline will be produced by treatment group with bars of the waterfall plot produced using different colours to represent prior radical prostatectomy or definitive external beam radiation (Yes, No). Per cohort, a spaghetti plot will display each participant's percentage change in PSA (e.g. each patient's baseline measurement will display as 100%) by the number of days since the day 1 dosing visit. On each participant's line, a marker will indicate the study day each dose occurred.

Example of this calculation of confirmed PSA response are displayed in Table 7 and Table 8.

Table 7: Calculation of PSA Response Example

Participant	Timepoint	Study Day	PSA Value (ng/mL)	PSA change from baseline	PSA absolute change from nadir	PSA percent change from nadir
1	Baseline	1	1.5			
1	Day 29	29	1.6	6.67%		
1	Day 57	57	1.0	-33.33%		
1	Day 64	64	0.9	-40.00%		
1	Month 4	122	0.8	-46.67%		
1	Month 5	153	0.2	-86.67%		
1	Month 6	164	0.2	-86.67%		
1	Month 7	215	0.3	-80.00%	0.1	50.00%
1	Month 8	246	0.3	-80.00%	0.1	50.00%
1	Month 9	271	0.5	-66.67%	0.3	150.00%

- Responder = Yes
- First observed PSA response = Month 5

- PSA progression (Defined in Section **Error! Reference source not found.**) = Month 9 (since there's a $\geq 25\%$ increase from PSA nadir AND an absolute increase of ≥ 0.2 ng/mL)
- Durable PSA response at Month 8 (Defined in Section 6.6.2.2) = Yes (since a confirmed PSA response has occurred and the criteria for PSA progression has not been met)

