Table 8: Calculation of PSA Response Example

Participant	Timepoint	Study Day	PSA Value (ng/mL)	PSA change from baseline	PSA absolute change from nadir	PSA percent change from nadir
1	Baseline	1	1.6			
1	Day 29	29	1.3	-18.75%		
1	Day 57	57	1.05	-34.38%		
1	Day 64	64	0.90	-43.75%		
1	Month 4	122	0.80	-50.00%		
1	Month 5	152	0.80	-50.00%		
1	Month 6	164	0.81	-49.38%	0.01	1.25%
1	Month 7	226	0.82	-48.75%	0.02	2.50%
1	Month 8	256	0.85	-46.88%	0.05	6.25%
1	Month 9	282	0.75	-53.13%	-0.05	-6.25%

- Responder = Yes
- First observed PSA response = Month 4
- PSA progression = No PSA progression
- Response at Month 8 = Yes (A confirmed PSA response has occurred and no PSA progression)

6.6.2.2. Durable PSA Response to VTP-850 at Month 8

If more than three participants have a confirmed PSA response at month 6 then the number, proportion and 90% CIs of participants with a durable PSA response (having a confirmed PSA response without PSA progression or on or before Month 8) will be presented for each treatment group using the EES. Participants with missing PSA data at Month 8 will have a durable PSA response imputed as described previously in Section 5.2.1. Otherwise, if participants are missing PSA data at Month 8 they will be treated as non-responders. The same summary will also be presented among participants who have a durable response at Month 6.

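### When Month 8 PSA is missing, SAP 5.2.1 can impute a durable response to a man whose PSA progression has already been observed

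*SAP*

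**What the plan says.** **The endpoint.** SAP 2.2.2.1 defines it as "Percentage of participants with confirmed PSA response compared to baseline without having PSA progression on or before Month 8". Protocol 11.2.3.2 agrees: "Durable PSA response is defined as having follow-up through Month 8 and a confirmed PSA response without having PSA progression" up to Month 8. It sets progression as a rise over nadir of at least 25% and at least 0.2 ng/mL. The Table 7 example in SAP 6.6.2.1 applies the same two-part test and calls the man durable at Month 8 "since a confirmed PSA response has occurred and the criteria for PSA progression has not been met".

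**The missing-data rule.** SAP 5.2.1 says that men without a Month 8 PSA "will have a durable PSA response imputed if they have a confirmed PSA response at the latest non-missing PSA collection preceding" Month 8 and at the first available PSA after it. All others with Month 8 missing count as non-responders. The paragraph defines a confirmed response as a fall of at least 50% from baseline on two consecutive measurements at least two weeks apart. It mentions neither nadir nor progression. SAP 6.6.2.2 adds no check of its own: "Participants with missing PSA data at Month 8 will have a durable PSA response imputed as described previously in Section 5.2.1".

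**When it applies.** The analysis is run "If more than three participants have a confirmed PSA response at month 6" (SAP 6.6.2.2). The Month 8 window is Days 226 to 255 (SAP Table 4); after a study pause, men "will have analysis visit assigned based on the recorded visit name in the eCRF" (SAP 5.1.4). Responders' PSA is collected after Month 6 "only until the start of new therapy such as ADT or development of unequivocal metastatic prostate cancer" (SAP 2.5).

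**The concern.** The endpoint has two conditions on different reference values: response is judged against baseline, progression against nadir. The imputation rule keeps the first and drops the second. After a deep fall, PSA can rise enough to be progression and still be less than half of baseline. For such a man the result depends on whether the Month 8 sample was taken, not on whether he progressed. No unobserved value has to be guessed here, because the rule sets aside progression that was recorded.

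The case can occur in practice. By SAP 2.5, PSA progression alone does not end sampling. Protocol 4.1.7 also provides for a responder who progresses more than two months after his last dose to stay in follow-up, possibly with a further dose. He can therefore have the later PSA that SAP 5.2.1 asks for.

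**Working it through.** **Inputs.** Response: PSA ≤ 0.5 × baseline, twice in a row, at least 14 days apart (SAP 5.2.1). Progression: PSA ≥ 1.25 × nadir and PSA ≥ nadir + 0.2 ng/mL (Protocol 11.2.3.2; SAP Table 7). The SAP does not formally define nadir. I took it as the lowest earlier value and assessed progression after the first 50% fall, which fits both SAP examples.

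**1. The SAP's own examples.** Table 7 (baseline 1.5, nadir 0.2) reproduces: first response Month 5, progression Month 9, durable. At Month 9 the PSA is 0.5:

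- from nadir: 0.5 − 0.2 = +0.3 ng/mL, and 0.3/0.2 = +150%, so progression;
- from baseline: (0.5 − 1.5)/1.5 = −66.67%, so still a response.

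The SAP's example therefore shows both states in one measurement. Table 8 also reproduces (first response Month 4, no progression, responder at Month 8).

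**2. Worked man.** Baseline and nadir are from Table 7. Visits are on target days, because Table 7's Months 5 and 6 are only 164 − 153 = 11 days apart.

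| Day | PSA (ng/mL) | From baseline | From nadir |
|---|---|---|---|
| 150 | 0.2 | −86.67% | nadir |
| 180 | 0.2 | −86.67% | 0 |
| 210 | 0.5 | −66.67% | +0.3, +150% |
| 240 | missing | | |
| 270 | 0.5 | −66.67% | +0.3, +150% |

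Response is confirmed at days 150 and 180 (30 days apart). Progression is observed at day 210.

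- By the endpoint definition: not durable.
- By SAP 5.2.1: durable. This holds whether a confirmed response at a collection means 50% below baseline on that day or a response already attained.
- With Month 8 observed at 0.5: not durable.

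**3. When the two states overlap.** With baseline B and nadir N, a PSA can satisfy both if

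max(1.25N, N + 0.2) ≤ 0.5B, that is, N ≤ 0.4B and N ≤ 0.5B − 0.2.

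| Baseline | Largest nadir | Smallest fall to nadir |
|---|---|---|
| 0.5 | 0.05 | 90% |
| 1.0 | 0.30 | 70% |
| 1.5 | 0.55 | 63.3% |
| 2.0 or more | 0.4B | 60% |

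At a baseline of 0.4 the limit is 0.5 × 0.4 − 0.2 = 0, so men at or below 0.4 ng/mL cannot be affected if their nadir is above zero. For B = 1.5 and N = 0.2, any PSA from 0.40 to 0.75 qualifies.

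**4. Effect of adding a progression check.**

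- Worked man: changes to not durable on both readings.
- Table 7 with day 246 removed: first progression is at day 271, so he stays durable, as the SAP says.
- Table 7 with Month 8 missing and Month 9 set to 1.4 ng/mL: non-responder before and after the change, on the day-of-visit reading.
- All 15⁴ = 50,625 sequences at days 150, 180, 210 and 270 (0.1 to 1.5 in steps of 0.1, B = 1.5, Month 8 missing): none becomes newly durable, and every changed sequence had progression observed before Month 8. This checks the logic only; it says nothing about frequency.

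**5. Size.** In a cohort of 6, one man is 1/6 = 16.7 points: for example 3/6 (Jeffreys 90% CI 0.209 to 0.791) becomes 4/6 (0.341 to 0.896). In a cohort of 3 it is 33.3 points. If 25 men are enrolled, with 3 in Cohort 1 and 6 in one full-dose cohort, the other has 25 − 3 − 6 = 16, and one man is 6.25 points.

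**The case against.** The best reply is that progression seen at Month 7 is not missing data. It settles the endpoint before any imputation, and SAP 6.6.2.2 carries the no-progression condition in its definition. A careful programmer might work that way. But SAP 6.6.2.2 itself sends every man without a Month 8 PSA to 5.2.1, the wording there is mandatory, and neither section gives the definition precedence. SAP 2.5 also says in general that missing PSA values are not imputed; the specific rule in 5.2.1 has to be taken as governing, though the two should be reconciled.

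The second reply is low weight, and much of that stands. An error needs more than three confirmed responders at Month 6, no PSA in a 30-day window that also accepts unscheduled samples, earlier observed progression, PSA still at or below half of baseline, and a later PSA. Men who leave after progressing have no later value and already count as non-responders. Regimen selection uses safety, opening Stage 2 uses PSA response rather than durable response, and Phase 2 will have its own SAP.

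Third, the rule can also err in the other direction. If the value labelled Month 8 is removed from Table 8, the preceding PSA is −48.75% from baseline. On the day-of-visit reading that man becomes a non-responder, although he never progresses. This is true, but it is a separate defect and does not excuse this one.

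**Conclusion.** The concern holds. SAP 5.2.1 contradicts the endpoint it serves: it can record a durable response for a man with observed PSA progression before Month 8. The error runs only in the product's favour. Each affected man moves his cohort's rate by 16.7 points at n = 6, with a range of 33.3 points at n = 3 to 6.25 at n = 16. The number affected cannot be estimated from the documents and may be zero.

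The conclusion rests on 5.2.1 being followed as written and on nadir being the lowest earlier value, as Tables 7 and 8 imply. Because the endpoint is descriptive and no stated decision depends on it, this should be corrected but does not threaten the trial.

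**What to change.** Keep the present condition in SAP 5.2.1, including the requirement at the first PSA after Month 8, and add:

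> *A durable response is imputed only if, in addition, no observed PSA on or before Month 8 meets the progression criteria (at least 25% and at least 0.2 ng/mL above nadir). A participant with progression observed on or before Month 8 is not durable, whether or not the Month 8 PSA is missing.*

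Repeat the condition in SAP 6.6.2.2, with nadir and progression derived as for men whose Month 8 PSA is present. Because it only adds a requirement, the change can turn an imputed durable response into not durable but never the reverse. Men whose progression is first seen after Month 8 are still handled by the existing before-and-after condition.

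In the same edit, repair the broken cross-reference to the progression definition in SAP 6.6.2.1, state the nadir rule, and reconcile the general no-imputation statement in SAP 2.5 with 5.2.1. The cost is a few sentences and minor programming, with no new data.

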5.2.2. Handling of Missing Safety Data

In general, missing clinical laboratory data, vital signs, and ECG data will not be imputed. Adverse event imputations for missing severity or relationship are given in Section 6.7.2. Unknown or partial medication and AE date imputations are given below and to be used only

for the assessment of prior / concomitant status for medications and treatment-emergent status for AEs.

5.2.3. Handling of Partial and Missing Dates for Adverse Events, Prior / Concomitant Medications, Missing Adenocarcinoma History Dates

Missing or Partial Adverse Event and Prior / Concomitant Medication Start Dates

Missing and / or incomplete dates for medications and AEs are imputed in a manner resulting in the earliest onset or the longest duration during the Treatment Period, whilst ensuring that the start date does not occur after the stop date. The stop date will not be imputed if the medication or AE is “Ongoing”. Technically, this will be done as follows:

For a missing / incomplete start date the earliest date of the following will be imputed:

- The later date of the earliest possible start date and the date of first dose of treatment.
- The latest possible start date (defined below).
- The latest possible stop date (defined below).

For a missing / incomplete stop date the latest date of the following will be imputed:

- The earlier date of the latest possible stop date and the date of last dose of treatment.
- The earliest possible stop date (defined below).
- The earliest possible start date (defined below).

Here, the earliest possible date is defined as:

- The date itself if available.
- The date of the first day of the month, if month and year are available but the day is missing.
- The date of the first day of the year, if year is available but day and month are missing.
- Day of informed consent, if the date is completely missing.

The latest possible date is defined as:

- The date itself if available.
- The date of the last day of the month, if month and year are available but the day is missing.
- The date of the last day of the year, if year is available but day and month are missing.
- Date of last known date on the study for the participant plus one year, if the date is completely missing.

Missing Adenocarcinoma History Dates

Missing adenocarcinoma history dates for the date of initial diagnosis of prostate adenocarcinoma, historic tumour sample collection date, radical prostatectomy date and date of nonmetastatic (M0) disease confirmed will be imputed as follows:

- The date itself if available.
- The date of the 15th of the month, if month and year are available but the day is missing.
- The date of 01-July of the year, if year is available but day and month are missing.
- No imputation, if the date is completely missing.

6. Statistical Methods

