4.1.1 Phase 1 – Dose/Regimen Finding Phase

Phase 1 will determine the recommended Phase 2 regimen (RP2R; dose level of both ChAdOx1-PCAQ and MVA-PCAQ, and route of administration of MVA-PCAQ) that will be used in Phase 2 and will follow a 3+3 design.

Participants will be dosed according to [Table 1](#) during the Screening and Intervention Periods [Table 5](#). The first 3 participants will be enrolled in Cohort 1. Enrolment of the first 3 participants in each cohort will be staggered by at least 9 days. The medical monitor will review the safety data for the previous participant, at least 7 days after the prime dose and after the first booster dose of VTP-850, before the corresponding dose is administered to the next participant. The safety review will include data from at least 7 days after each ChAdOx1-PCAQ prime dose; at least 7 days after the first booster MVA-PCAQ dose if administered IM; and at least 14 days after the first booster dose of MVA-PCAQ if administered IV. If 1 or more of the 3 participants has a dose limiting toxicity (DLT), 3 additional participants may be enrolled into Cohort 1. If there is no DLT after the first dose of VTP-850 in the first 3 participants, 3 participants will be enrolled into each of Cohorts 2 and 3 concurrently, with the first participants in Cohorts 2 and 3 staggered by at least 9 days to allow for medical review.

If DLT is not seen in more than 1 participant in Cohort 2 after the first dose of VTP-850, then an additional 3 participants will be enrolled into Cohort 2. Safety data for the DLT period following each booster dose will be assessed by the medical monitor prior to the corresponding booster dose being administered to additional participants.

If DLT is not seen after the first dose of VTP-850 in more than 1 participant in Cohort 3, then an additional 3 participants will be enrolled into Cohort 3. Safety data for the DLT period following each booster dose will be assessed by the medical monitor prior to the corresponding booster dose being administered to additional participants.

A total of 6 participants in each of Cohorts 2 and 3 will be dosed with MVA-PCAQ on Day 29 and Day 57. Therefore, participants who withdraw before dosing, before completion of dosing or who have dose delays will be replaced (unless the reason for not completing dosing per protocol is related to a stopping rule criteria being met).

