2.2.1.1. Endpoints for the Primary Objective(s)

- Number and proportion of participants with AEs, treatment-related AEs, \geq Grade 3 AEs, \geq Grade 3 treatment-related AEs, serious adverse events, and treatment-related serious adverse events
- Number and proportion of participants with clinically significant laboratory values
- Change from baseline for laboratory tests, electrocardiogram and vital sign measurements at each time point of collection

Full details for each endpoint are provided in Section 6.7.

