2.3. Sample Size and Power

A total of approximately 144 participants will be enrolled. Approximately 25 participants will be enrolled into the Phase 1 of the study. A sample size of approximately 125 participants will be eligible for inclusion in the Phase 2 efficacy evaluation. Full details of the sample size calculation are provided in the protocol Section 11.4.

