3.1.6. Population-level Summary for Comparison between Treatment Conditions

The treatment effect will be quantified by the number and proportion of participants in each treatment group with adverse events, treatment-related adverse events, \geq Grade 3 AEs, \geq Grade 3 treatment-related AEs, serious adverse events and treatment-related serious adverse events. No formal hypothesis testing will be conducted.

4. Analysis Populations

In accordance with ICH E3 and E9³, the following analysis sets will be used for the analyses. The assignment of participants to the analysis sets (and whether any participant or specific data from a participant is excluded) will be determined at the pre-database-lock Data Review meeting.

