6.7.2. Adverse Events

All AEs recorded on the eCRF will be coded using the MedDRA dictionary [version 25.1 or later]:

- Treatment-emergent AEs (TEAEs) are events with start date on or after the first dose of VTP-850 and reported as not starting before first treatment.
- Treatment-Emergent Serious AEs (TESAEs) will be defined as TEAEs regarded by the investigator as Serious = “Yes”.
- The relationship between a TEAE and VTP-850 is assessed as related or not related. A treatment-related TEAE will be defined as a TEAE considered by the investigator related to treatment.

- Assessment of AE severity / intensity will be based on the National Cancer Institute-Common Terminology Criteria for AEs (NCI-CTCAE⁴, version 5.0). Severe TEAEs are defined as TEAEs assessed as being “Grade 3 / Grade 4 / Grade 5” in intensity.
- TEAEs leading to discontinuation of treatment are defined as TEAEs where “Action Taken With Study Treatment” is indicated as “Drug Withdrawn”.

Adverse events will be summarized for the Safety Analysis Set by treatment group and overall as follows:

- An overview of TEAEs including the number and percentage of participants with at least one of each mentioned TEAE type:
 - Any TEAE
 - Leading to discontinuation of study treatment
 - Leading to death
 - Grade 1 severity (mild)
 - Grade 2 severity (moderate)
 - Grade 3 severity (severe)
 - Grade 4 severity (life-threatening or disabling)
 - Grade 5 severity (death related to TEAE)
 - Any study treatment-related TEAE
 - Leading to discontinuation of study treatment
 - Leading to death
 - Any serious TEAE
 - Leading to death
 - Any serious study treatment-related TEAE
 - Leading to death
- The number and percentage of participants reporting each TEAE and the count of number of events will be summarized by SOC and PT for the following types of TEAEs:
 - TEAEs
 - TEAEs Leading to Discontinuation of Study Treatment
 - TEAEs Leading to Death
 - TEAEs by Maximum Severity
 - Treatment-related TEAEs
 - Treatment-related TEAEs by Maximum Severity
 - Treatment-related TEAEs Leading to Discontinuation of Study Treatment
 - Treatment-related TEAEs Leading to Death
 - Serious TEAEs
 - Serious TEAEs Leading to Discontinuation of Study Treatment
 - Serious TEAEs Leading to Death
 - Study Treatment Related Serious TEAEs
 - Study Treatment Related Serious TEAEs Leading to Death

- Study Treatment Related Serious TEAEs Leading to Discontinuation of Study Treatment
-

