- The number and percentage of participants who died will be summarized by the primary reason of death.

In the above summaries, participants with more than one TEAE within a particular SOC are counted only once for that SOC. Similarly, participants with more than one TEAE within a particular PT are counted only once for that PT, respectively. Overall summaries of “Any TEAE” and “Any study treatment-related TEAE” will only include participants at the maximum severity.

For summaries by maximum severity, participants with multiple TEAEs within a particular SOC or PT will be counted under the category of their most severe TEAE within that SOC or PT. TEAEs with missing severity will be included in the counts of the ‘Number of Participants with at least one TEAE’, ‘System Organ Class’ and ‘Preferred Term’ rows of the summary but they will not be included in the counts by severity.

The following tables will also be presented by administration (i.e. ChAdOx1-PCAQ dose, 1st MVA-PCAQ dose, 2nd MVA-PCAQ dose, 3rd MVA-PCAQ dose), for TEAEs that start within 28 days of each administration (e.g. summarizing TEAEs which occurred from ChAdOx1-PCAQ dose up to the earliest of 1st MVA-PCAQ dose or 28 days following the first dose). The denominator will be the number of participants who have received that dose:

- TEAEs
- TEAEs by Maximum Severity
- Treatment-related TEAEs
- Treatment-related TEAEs by Maximum Severity
- Serious TEAEs
- Study Treatment Related Serious TEAEs

Summaries by SOCs and PTs will be sorted by SOCs alphabetically (MedDRA) and PTs within SOC by descending order of total incidence. Where preferred terms tie, PTs will be sorted alphabetically.

No statistical comparisons of AEs between treatment groups will be performed.

All AE data will be listed using the Safety Analysis Set. Treatment-emergence status will be flagged in the listing. The listing will present the relative start and stop day of the AE calculated relative to the first dose of treatment. If the AE is “Ongoing” it will be indicated as such in the listing and the relative stop day will not be calculated.

In addition, the following listings will be presented:

- Listing of Deaths
- Listing of Serious TEAEs
- Listing of AEs Leading to Discontinuation of Study Treatment

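### SAP 5.2.2 refers to 6.7.2 for imputation of missing AE severity and relationship, but 6.7.2 has none; any such gap can only lower the Grade 3+ and treatment-related proportions

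*SAP*

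**What the plan says.** SAP 5.2.2 sets the general rule that missing laboratory, vital-sign and ECG data are not imputed. For adverse events it then says: "Adverse event imputations for missing severity or relationship are given in Section 6.7.2".

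Section 6.7.2 deals with the two fields as follows.

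- **Severity.** A TEAE with missing severity stays in the rows for participants with at least one TEAE, for system organ class and for preferred term, "but they will not be included in the counts by severity".
- **Relationship.** "The relationship between a TEAE and VTP-850 is assessed as related or not related". The section adds: "A treatment-related TEAE will be defined as a TEAE considered by the investigator related to treatment". It does not say what happens when the field is blank.

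Both fields feed the primary endpoint. SAP 2.2.1.1 opens its list with "Number and proportion of participants with AEs, treatment-related AEs" and continues through Grade 3 or higher AEs, Grade 3 or higher treatment-related AEs, SAEs and treatment-related SAEs. SAP 3.1.6 uses the same proportions as the population-level summary of the primary estimand and adds: "No formal hypothesis testing will be conducted".

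**The concern.** A programmer cannot satisfy both sections: 5.2.2 points to an imputation rule, and 6.7.2 gives an exclusion for one field and silence for the other. If the rule is settled only once the blank records are known, the choice is post hoc and falls on the primary endpoint.

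The direction also matters. Elsewhere the SAP handles missing data cautiously. Partial AE dates are imputed towards the earliest onset or longest duration (5.2.3). A missing Month 8 PSA counts as non-response unless the values on either side support a response (5.2.1). For AE grade and relationship, the text of 6.7.2 works the other way, towards a more favourable safety profile, in a first-in-human trial with small cohorts. Protocol 11.2.1 also commits the SAP to account for missing data and its possible impact, and for these two fields it does not.

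**Working it through.** The primary endpoint has no test, alpha or power, so there is no plan figure to reproduce. The check is a comparison of texts followed by simple arithmetic.

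**Step 1: promise against content**

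| Field | SAP 5.2.2 | SAP 6.7.2 | Effect of a blank |
|---|---|---|---|
| Severity | Imputation is in 6.7.2 | Left out of the counts by severity | Event cannot count as Grade 3+ |
| Relationship | Imputation is in 6.7.2 | No rule; related means judged related by the investigator | By default the event does not count as related |

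The effect for relationship is an inference from the definition; no sentence states it.

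**Step 2: direction**

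By default SAP 6.1 takes the number of participants in the analysis population as the denominator. A participant whose only qualifying event has a blank field therefore stays in the denominator and leaves the numerator. The proportion falls or is unchanged; it cannot rise.

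**Step 3: which endpoints can move**

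- Any AE and any SAE: no change, since neither depends on grade or relationship.
- Grade 3+ AEs: missing severity.
- Treatment-related AEs and treatment-related SAEs: missing relationship.
- Grade 3+ treatment-related AEs: either field.

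An understatement needs three things together: the field is still blank at lock, the event truly qualifies, and the participant has no other fully recorded qualifying event.

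**Step 4: size of one affected participant**

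The shift is 1/N, where N is the group's Safety Analysis Set (everyone given at least one dose, SAP 4.3).

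- N = 3: 1/3 = 33.3 percentage points
- N = 6: 1/6 = 16.7 points
- N = 25 (all of Phase 1): 1/25 = 4.0 points

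The value N = 6 is not the safety denominator by design. Protocol 4.1.1 says "A total of 6 participants in each of Cohorts 2 and 3 will be dosed with MVA-PCAQ on Day 29 and Day 57", which counts participants dosed on both booster days. Those who withdraw or are delayed are replaced, and any who were dosed stay in the safety set. SAP 2.3 says: "Approximately 25 participants will be enrolled into the Phase 1 of the study". With 3 to 6 in Cohort 1, 25 − 6 = 19 to 25 − 3 = 22 remain for Cohorts 2 and 3. If all are dosed and split evenly (an assumption), N is 9.5 to 11 per group, and one participant is 1/11 = 9.1 to 1/9.5 = 10.5 points. The split need not be even, because SAP 6.1 places anyone without a second dose in the IM/IM Full group.

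**Step 5: expected shortfall, illustration only**

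Let π be the true proportion of participants with exactly one qualifying event, and m the chance that its field is blank, independent of everything else. The expected shortfall is π × m. Neither value is in the documents; the ranges below are assumed.

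| π | m = 0% | m = 1% | m = 5% | m = 10% |
|---|---|---|---|---|
| 10% | 0 | 0.1 | 0.5 | 1.0 |
| 20% | 0 | 0.2 | 1.0 | 2.0 |
| 33% | 0 | 0.33 | 1.65 | 3.3 |

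(Shortfall in percentage points.) With no missing fields the shortfall is zero.

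**The case against.** The strongest reply is that blanks should be rare and would not be hidden. Protocol Appendix 3 requires the investigator to assess severity and relationship for AEs, and relationship is a yes/no question. SAEs and AESIs are assessed by sponsor and investigator, and deaths get narratives and a listing. Events with missing severity stay in the any-TEAE, organ-class and preferred-term rows, all AE data are listed, and SAP 6.1 allows a missing category where appropriate. In a trial of this size a reader could find the blanks. All of this stands and limits the likely size. It does not supply the rule that 5.2.2 promises. Section 6.7.2 does not call for a missing row, and a listing does not correct a reported proportion.

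Three stronger readings are tempting, and the documents do not support them.

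- *That the primary counts are biased low.* No missing rate is given, and with complete fields there is no effect.
- *That the choice of Phase 2 regimen is distorted.* Protocol 4.1.1 gives that choice to the Safety Monitoring Committee, on cumulative safety data and its evaluation of DLTs. SAP 6.7.8 treats those reviews as separate from the SAP's analyses. Nothing ties the choice to the final TEAE tables.
- *That the effect is 16.7 points.* That is the step size of one participant in a group of six, and the safety set may be larger.

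It can also be objected that counting every blank severity as Grade 3 in the main table would replace a possible undercount with upward-only handling. That is fair, and it is why the fix treats the two fields differently.

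**Conclusion.** The inconsistency is confirmed. The imputation that 5.2.2 refers to does not exist: missing severity is expressly excluded from the severity counts, and missing relationship has no rule. As written, the Grade 3+, treatment-related, Grade 3+ treatment-related and treatment-related SAE proportions would be understated if a decisive field is missing at lock, and would otherwise be correct.

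The direction rests on the SAP 6.1 default denominator and on reading a blank relationship as outside the definition of related. The size is not determinable from the documents beyond the 1/N step per affected participant. The SAP should be corrected before database lock because the primary endpoint is involved and the correction is cheap, not because a material bias has been shown.

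**What to change.** Add the missing rules to SAP 6.7.2 so that the reference in 5.2.2 is true:

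1. A TEAE with missing relationship is counted as related.
2. A TEAE with missing severity appears in a 'Missing' row of the severity tables. The Grade 3+ proportions (all and treatment-related) are also given under a worst case in which missing severity counts as Grade 3 or higher, and as Grade 5 if the event was fatal.
3. A footnote gives the number of records affected in each table, and the listings show the raw values as missing.

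Reword 5.2.2 to match, since missing severity would then be displayed and bounded, not imputed in the main table.

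The cost is a few sentences in the SAP plus a row and a footnote in the table shells. No new data are needed. The downside is small: a minor event with a blank field may be over-counted, as related in the main table or as Grade 3+ in the worst case, and the footnote shows how often. If no fields are missing, the results do not change.
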